STUDY DESIGN. This study is a prospective pragmatic pilot trial to generate data needed to inform a fully-powered longitudinal study consisting of nurses across a wider geographic region. There are 4 study components:

1. Electronic Quantitative Surveys (baseline, Week 4 & Week 8) will consist of demographic questions and validated measures for personal characteristics, sleep, stressful life events, psychiatric characteristics, work environment factors, and all psychological health outcomes. (**Table 1**). The surveys will be administered 3 times (baseline, week 4 and week 8) to generate pilot longitudinal data.

2. Psychological Assessment (baseline). To confirm a preexisting psychiatric diagnosis, a *Structured Clinical interview for DSM-5 Diagnosis* (Research version) (SCID-5-RV) will be administered in-person by a Psychiatric Mental Health Nurse Practitioner (PMHNP) at baseline. SCID-5-RV is a semi-structured interview guide for making major DSM-5 diagnoses such as mood disorders, psychotic symptoms, substance use, sleep, and trauma- or stressor-related disorders and takes approximately 45-60 minutes to administer. Studies suggest that prior history of mental illness, such as depression, has been linked to suicide.

3. Physiologic Biomarkers (Weeks 1-8). Heart rate and sleep (hours/day) will be collected using a wearable device, *Oura ring*[®], a piece of jewelry that can be custom fit to each participant. Heart rate variability (HRV), a highly sensitive physiologic metric for stress, is the constant variation in milliseconds between beats, and controlled by the autonomic nervous system. Low HRV is a strong indicator of physiologic stress (fight or flight response) and has been associated with increased risk for suicide attempt. Studies have demonstrated high validity in the assessment of HRV and sleep using the *Oura ring*[®]. The device will also collect activity levels (steps/day) and sleep cycles, known confounders for stress levels.

TABLE 1. Study Variables and Measures

Variable	Operational Definition	Measure
Demographics	Age, Sex, Gender, Race, Ethnicity, marital status, household income, parental status, smoking history, substance use; years of nursing experience	Validated single-items
Sleep	Sleep quality and duration	Pittsburgh Sleep Quality Index ⁴⁴ ($\alpha = .83$) Oura ring [®] Somni [®] 14
Stress	Self-reported stress Heart Rate Variability	Perceived Stress Scale ⁴⁵ ($\alpha = .76$) Oura ring [®]

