4. Sleep Intervention (Weeks 4-8) *Somni*[®] is an evidence-based personalized sleep intervention aimed at promoting optimal sleep health and has demonstrated effectiveness in shift workers outside the healthcare sector (e.g. Disney). *Somni*[®] consists of a sleep kit and a smart phone application. The sleep kit is box of items with demonstrated past evidence of improving sleep health: Blue light blocking glasses, white noise machine, lavender spray, ear plugs, light blocking eye mask, and herbal tea. Rather than dictate a “one size fits all” approach to optimize sleep health, there is current evidence that individualized sleep interventions are recommended to optimize sleep quality. *Somni*[®] permits individualized sleep quality promotion and participants are able to select their preferred use, timing, and duration of each of the box contents. The kit is accompanied by a *Somni*[®] smartphone app that prompts participants to input the use of each component in the kit and provide a subjective sleep quality rating each day. Drs. [name] and [name] have partnered with the developers of *Somni*[®] who will provide free sleep kits and app access to our study participants. The *Somni*[®] app is interoperable with the *Oura Ring*[®] and will automatically sync all physiologic and sleep data together in one location, fully accessible to the participants, and displayed in graphs in the *Somni*[®] app that are easy to read and interpret (e.g. total daily steps; daily sleep hours). *Somni*[®] will be implemented Weeks 4 through 8 to investigate its preliminary impact on stress and suicidal ideation by comparing survey and physiologic metrics from Weeks 1-4.

STATISTICAL ANALYSIS

First, we will calculate composite scores of individual measures (sleep, stressful life events, psychiatric characteristics, and work environment characteristics). Descriptive statistics will be calculated including means

and standard deviations (normally distributed values), median and interquartile range (non- normally distributed variables), or absolute and relative frequencies (categorical variables). Outliers and missing data will be assessed (outliers > 3 standard deviations from the mean will be removed). Significance level will be set at $\alpha = 0.05$.

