Aim 3. We will calculate descriptive statistics, percentages, and frequencies for 1) each *Somni*[®] sleep kit component 2) subjective sleep quality via *Somni*[®] app 3) global sleep scores (PSQI score) and HRV. We will test differences in global sleep scores (PSQI), mean sleep duration (Oura ring), mean subjective sleep quality and use of sleep kit components at the individual level between the 3 data points. We will report the effect sizes and will test for significance in the model for each psychosocial and work environment factor, each *Somni*[®] sleep kit component (mean weekly frequency), and the mean PSQI score while controlling for age, sex, gender, race, and history of psychiatric diagnosis. We will repeat the same analysis modeling mean C-SSRS as the dependent variable. To evaluate the change in suicidal behavior over time and the impact of global sleep (PSQI score) and each *Somni*[®] sleep kit component (mean weekly frequency), we will fit conditional latent growth curve models.

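### Aim 3 reduces self-chosen, daily-logged kit use to a mean weekly frequency, so its component coefficients can reflect who chooses an item; a nightly and a pre-kit-adjusted analysis should be added

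*Combined protocol and SAP*

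**What the plan says.** Study Design, component 4 (Sleep Intervention), describes a kit of six items: "Blue light blocking glasses, white noise machine, lavender spray, ear plugs, light blocking eye mask, and herbal tea". Use is not assigned: "participants are able to select their preferred use, timing, and duration of each of the box contents". The app "prompts participants to input the use of each component in the kit and provide a subjective sleep quality rating each day". The wearable also runs daily (Study Design, component 3): "Heart rate and sleep (hours/day) will be collected using a wearable device", and Table 1 takes HRV from the same ring. The app "will automatically sync all physiologic and sleep data together in one location". A record by nurse and by night should therefore exist for the kit period.

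Statistical Analysis, Aim 3, will test for significance each "sleep kit component (mean weekly frequency), and the mean PSQI score while controlling for age, sex, gender, race, and history of psychiatric diagnosis". It then adds: "We will repeat the same analysis modeling mean C-SSRS as the dependent variable". The growth curves for suicidal behavior take component use in the same averaged form.

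The plan also has comparisons within nurses. The intervention "will be implemented Weeks 4 through 8 to investigate its preliminary impact on stress and suicidal ideation by comparing survey and physiologic metrics from Weeks" 1 to 4. Aim 3 tests differences in PSQI, ring sleep duration, app rating and kit use across the three data points at the individual level.

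**The concern.** Kit use is a choice, and how well a nurse usually sleeps is an obvious reason for it. If poor sleepers reach for an item more often, a comparison of heavier with lighter users carries that difference into the item's coefficient. A useful item can look useless or harmful. If good sleepers are the keener users, an inert item can look useful. Age, sex, gender, race and psychiatric history remove this only so far as they stand in for usual sleep.

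Averaging also sets aside the night-to-night variation in use that the app collects. The pilot is meant to inform a larger study, so a component table read as item effects could steer which items go forward.

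**Working it through.** The plan states no sample size, SD, effect size or distribution of use, so there is no figure of its own to reproduce. The check is a reading of the text, followed by an illustration on assumed inputs.

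**1. What each planned analysis can say about a component**

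| Planned analysis | Form of kit use | Contrast |
|---|---|---|
| Significance-test model, and its repeat for mean C-SSRS | Mean weekly frequency | Between nurses, inferred from an averaged predictor, a mean outcome and fixed nurse covariates |
| Growth curves for suicidal behavior | Mean weekly frequency | Trajectories of heavier against lighter users |
| Weeks 4-8 against Weeks 1-4, and the three data points | Not a predictor | Within nurse, but no component association |

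No row compares a nurse's nights with and without an item, or relates her change from pre-kit values to her use.

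**2. Size of the between-nurse distortion**

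For one item, the slope of nurse-mean sleep on nurse-mean use is approximately

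slope = d + r × SD_nurse / SD_use.

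Assumed inputs: true gain on nights of use d = 0.20 h; SD of usual sleep between nurses 0.8 h; SD of mean use (proportion of nights) 0.25; r = correlation of mean use with usual sleep.

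- r = 0: 0.20 h
- r = -0.1: 0.20 - 0.1 × 0.8/0.25 = 0.20 - 0.32 = -0.12 h
- r = -0.3: 0.20 - 0.96 = -0.76 h
- r = -0.5: 0.20 - 1.60 = -1.40 h
- r = +0.3: 0.20 + 0.96 = 1.16 h

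The sign turns at r = -0.20 × 0.25/0.8 = -0.0625. The spread of use matters. At r = -0.3 the slope is 0.20 - 0.24/0.18 = -1.13 h for SD_use 0.18, and 0.20 - 0.24/0.37 = -0.45 h for SD_use 0.37. Simulations that apply r to the underlying propensity, of which a 28-night average is a noisy measure, give somewhat smaller distortions: -0.98, -0.69 and -0.39 h for SD_use 0.18, 0.25 and 0.37.

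In a separate simulation (between-nurse SD 1, nightly SD 1, no true effect), the nurse-mean model rejected at 0.05 in about 41-43% of samples of 40 nurses and 81% of samples of 100 when r was ±0.3. At r = 0 it rejected in 4-5%.

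**3. Precision of the alternatives**

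Assume 50 nurses, 28 kit nights, night-to-night SD 1.2 h and average use 50%.

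- Between nurses (r = 0): SE = √(0.8² + 1.2²/28) / (0.25 × √50) = 0.831/1.768 = 0.47 h
- Change from 28 pre-kit nights on mean use: SE = √(2 × 1.2²/28) / 1.768 = 0.321/1.768 = 0.18 h
- Nightly, within nurse: variance of use within nurse = 0.25 - 0.25² = 0.1875, so SE = 1.2/√(50 × 27 × 0.1875) = 1.2/15.9 = 0.075 h

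The last two centre on 0.20 h if selection depends only on stable traits.

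**4. Where the nightly contrast fails**

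Suppose a nurse with 50% average use takes an item on 55% of nights that are 1 SD bad and 45% of nights that are 1 SD good. The covariance of use with that night's sleep is -0.05 × 1.2 = -0.06, and the variance of use is 0.25. The shift is -0.06/0.25 = -0.24 h, so the estimate becomes 0.20 - 0.24 = -0.04 h. The separate simulation agrees in direction: with 100 nurses, a true 0.30 became 0.06 under moderate and -0.12 under strong dependence on the night. In the same runs, change from pre-kit values gave 0.26 and 0.22.

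**The case against.** The strongest reply is that the plan already uses each nurse as her own control, through the before/after comparison and the three data points. Its growth curves, as set out for Aim 2, carry random intercepts and slopes. Psychiatric history is controlled, and PSQI appears beside the components. The psychosocial and work environment factors may sit in the same model. This is also an exploratory aim of a pilot.

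Much of that stands. A reader might infer that single nights offer the only own-control contrast; the before/after comparisons show otherwise. Those comparisons do not, however, estimate a component's association with anything. The growth curves are less exposed to stable differences but still set users against non-users. Whether mean PSQI is a predictor or an outcome in the significance-test model is unclear. If it is a predictor averaged over all three surveys, it includes Week 8 and is not a clean pre-kit adjustment.

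A second reply is that the nightly model has its own bias, since nurses also choose the timing. That stands too, as step 4 shows, and it is why a pre-kit companion analysis is needed beside it.

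A third is that the illustration uses ring sleep hours, whereas the outcomes named around mean weekly frequency are C-SSRS and, on one reading, PSQI. This is correct. The hours show the mechanism and do not forecast those coefficients.

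**Conclusion.** The concern holds in a limited form. On the natural reading of an unwritten model, the mean-weekly-frequency coefficients compare nurses who chose different amounts of use, with no pre-kit sleep among the named controls, and the daily data are not used for components. On the assumed inputs, a weak correlation between use and usual sleep (about -0.06) is enough to change the sign, and -0.3 gives roughly -0.4 to -1.1 h against a true 0.20 h. Every input is an assumption; the documents support no particular correlation, spread of use or sample size.

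A reader might go further and infer that the planned coefficients will be wrong, or that a nightly analysis would recover the true item effect. The documents support neither. How strongly use follows usual sleep is unknown, and free choice of timing leaves the nightly estimate open to confounding. This is a worthwhile, inexpensive improvement and does not invalidate the pilot.

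**What to change.** 1. **Nightly model, Weeks 4-8.** For ring sleep duration, ring HRV and the app's daily rating, fit a nurse-by-night mixed model with a random nurse intercept. Enter all six items together, each as that night's deviation from the nurse's own mean, with her mean use as a separate term. Adjust for study day, prior-night sleep and survey-reported shift type. Shift type is a survey item and no nightly shift log is described, so it will mainly adjust the nurse-mean term. State that a night without an app entry is missing, not a night of non-use.
2. **Pre-kit companion.** Relate change from the nurse's own Weeks 1-4 ring sleep and HRV, and from Week 4 PSQI, to mean use, or adjust the mean-frequency models for those values. Week 4 falls in both periods, so define pre-kit values as those taken before the kit is in use. If nurses take up items after a chance run of bad nights, regression to the mean can flatter this contrast.
3. **Labelling.** Write out the Aim 3 model, say whether PSQI is an outcome or a predictor, and label the mean-weekly-frequency coefficients for PSQI and C-SSRS as descriptive of users, not as item effects. These outcomes come from three surveys, so no nightly analysis of them is possible.

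The cost is SAP text and some added analysis on data already being collected, assuming HRV can be exported by night. The remaining weakness should be stated in the SAP: using an item because a bad night is expected can bias the nightly estimate, even to the wrong sign, so all component results remain associational.

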COVER PAGE

NCT06079853

Date of Protocol Approval: 10/18/2023

Study Title: The Use of Physiologic Measures and Sleep Health Promotion to Identify and Mitigate Predisposing Factors of Suicidal Ideation in Nurses

PI: [name], RN, ANP-BC, FAAN

PI Contact: [contact]

Sponsor: Columbia University School of Nursing

STUDY PROTOCOL

The purpose of this study is to generate longitudinal pilot data that investigates 1) which factors (stressful life events, psychiatric characteristics, and work environment characteristics) are associated with stress and subsequent suicidal ideation; and 2) to explore the preliminary impact of an existing evidence-based sleep intervention, *Somni*^{®14}, on stress, psychological health, and suicidal ideation in working nursing professionals. The specific aims are:

Aim 1. To investigate associations between sleep, stressful life events (life stressors, discrimination, lateral violence), psychiatric characteristics (psychiatric diagnosis, subjective mood), work environment characteristics (workload, shift type and duration, overtime, nurse work environment, and team relations) and stress (self-reported and heart rate variability) in working nursing professionals while controlling for standard covariates known to influence stress. *Hypothesis 1:* Suboptimal work environment characteristics are positively associated with self-report and physiologic indicators of stress [heart rate variability (HRV)]. *Hypothesis 2:* Poor sleep (duration and quality) will be positively associated with self-report and physiologic indicators of stress (HRV).

Aim 2. To determine if stress exposure (self-report and HRV) are associated with predisposing factors (sleep, stressful life events, additional psychiatric characteristics, and work environment characteristics), and to explore whether stress mediates the effect of predisposing factors on suicidal ideation in working nursing professionals. *Hypothesis:* Nurses with low HRV are at higher risk for suicidal behavior when exposed to poor sleep, the presence of psychiatric characteristics (e.g. Depression), stressful life events, or suboptimal work environment characteristics (e.g., poor team relations).

Exploratory Aim. To explore the preliminary impact of an existing sleep intervention (*Somni*[®]) on self-reported stress, HRV, sleep, and psychiatric health outcomes including depression, burnout, and suicidal ideation.

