Suicidal Ideation	Suicidal Ideation	Columbia-Suicide Severity Rating Scale ⁴⁶ ($\alpha = .94$)
Stressful Life Events		
Life Stressors	43-item checklist to assess changes in life (e.g. divorce; death of friend)	Holmes & Rahe Stress Scale ⁴⁷
Discrimination	Perceived discrimination	Perceived Discrimination Scale ⁴⁸ ($\alpha = .93$)
Lateral Violence	Bullying/incivility	Negative Acts Questionnaire-Revised ⁴⁹ ($\alpha = .90$)
Psychiatric Characteristics		
Psychiatric Diagnosis	Psychiatric Diagnosis	SCID-5-RV (Research Version) ⁴²
Subjective Mood	Depression Burnout	Beck's Depression Index-II ⁵⁰ ($\alpha = .91$) Maslach Burnout Inventory-HSS ⁵¹ ($\alpha = .91$)
Work Environment Characteristics		
Workload	Perceived workload Overtime RN-patient staffing ratio	NASA Task Load Index ⁵² ($\alpha = .80$) Self-reported number of hours Standard ratio; frequency of shifts above standard
Shift Work	Shift type (day or night shift) Shift duration (hours)	Validated single-items Self-reported mean hours/shift Number of quarterly overtime hours
Practice Environment	Nurse Participation; quality of care; management and leadership; human resources; nurse-physician relations	Practice Environment Scale-Nursing Work Index ⁷ ($\alpha = .80$)
Team Relations	Clinician team cohesiveness	Provider Co-management Index ²⁷ ($\alpha = .96$)

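### The plan does not say that period-specific shift type and overtime enter the before-after Somni comparison, and neither overtime item is tied to a 4-week period

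*Combined protocol and SAP*

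**What the plan says.** **Comparison.** STUDY DESIGN, component 4, schedules Somni for Weeks 4 through 8 "to investigate its preliminary impact on stress and suicidal ideation by comparing survey and physiologic metrics from Weeks 1-4". Each nurse's own earlier weeks are the comparator.

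**Analyses.** STATISTICAL ANALYSIS, Aim 3, which serves the Exploratory Aim, describes three:

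- Tests of change in PSQI, ring sleep duration, subjective sleep quality and "use of sleep kit components at the individual level between the 3 data points". No covariates are named.
- An association model that will "test for significance in the model for each psychosocial and work environment factor", as well as for kit components and PSQI, "while controlling for age, sex, gender, race, and history of psychiatric diagnosis". It is repeated with C-SSRS as the outcome.
- A conditional growth model for suicidal behavior, with PSQI and kit-component frequency as the only named predictors.

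**Work variables.** The specific aims (Aim 1) define "work environment characteristics (workload, shift type and duration, overtime, nurse work environment, and team relations", so shift type and overtime belong to the factors that the association model tests. They can be collected repeatedly: "The surveys will be administered 3 times (baseline, week 4 and week 8) to generate pilot longitudinal data". TABLE 1 lists overtime twice: under Shift Work as "Number of quarterly overtime hours", and under Workload as a self-reported count of hours with no stated window. Shift type is recorded as day or night.

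**The concern.** In a single-group before-after design, anything that changes in a net direction between the periods becomes part of the estimated effect. For working nurses, shift pattern and overtime are obvious candidates. The plan itself treats them as possible drivers of stress, and they can change within 8 weeks. The traits named as controls cannot, so adjusting for them does not protect the contrast.

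A net move off nights, or a fall in overtime, after Week 4 could look like better sleep, lower stress or lower C-SSRS scores due to Somni. A move the other way could hide a benefit. The pilot is meant to inform a fully powered study, so such an artefact could carry over into that design. If the survey items are not tied to the two periods, the gap cannot be repaired at analysis.

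**Working it through.** The plan states no sample size, effect size or SD, so it has no figure to reproduce. All sizes below rest on assumptions.

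**1. What each kind of covariate can do.** For nurse *i* in period *t* (1 = before, 2 = Somni), write

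Y_it = a_i + δ·Somni_t + γ·S_it + β′Z_i + e_it,

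where S is a work variable, such as being on nights, and Z holds the fixed traits. The within-nurse difference is

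d_i = δ + γ(S_i2 − S_i1) + (e_i2 − e_i1).

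β′Z_i cancels. The mean of d estimates δ + γ × (net change in S). So the bias is γ × net change, and it is zero when changes balance out. In one simulated balanced data set the before-after contrast was 0.0375 both with and without age and sex in the model.

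**2. Size for sleep duration.** Assume that leaving nights adds 0.5 to 1.0 h (30 to 60 min) of sleep, and that a net 5% to 20% of nurses leave nights after Week 4:

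- low: 0.05 × 30 = 1.5 min
- high: 0.20 × 60 = 12 min
- no net change: 0 min

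**3. Effect on the test.** A paired simulation used an assumed 40 nurses, 400 runs, a true Somni effect of 0, a night-shift effect of 0.5 outcome units, a between-nurse SD of 0.7 and a residual SD of 0.5.

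| Shift changes | Shift term | Mean contrast | Rejections at 0.05 |
|---|---|---|---|
| Net 20-point fall in nights | none | 0.099 | 14% |
| Net 20-point fall in nights | time-varying | 0.002 | 6% |
| Balanced | none | −0.009 | about 4% |

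The first row agrees with the formula: 0.20 × 0.5 = 0.10. With 400 runs, the Monte Carlo standard error is √(0.14 × 0.86 / 400) = 1.7 points for the 14%, and √(0.06 × 0.94 / 400) = 1.2 points for the 6%. The 6% is therefore compatible with 5%, and the 14% is not.

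**4. The quarterly overtime item.** Assume that quarterly means a rolling 13 weeks ending at the survey. At Week 8 the window covers 13 − 8 = 5 pre-study weeks, 4 comparison weeks and 4 Somni weeks, so the Somni share is 4/13 = 31%. The Week 4 and Week 8 windows share 13 − 4 = 9 weeks, or 9/13 = 69%. If a calendar quarter is meant, these fractions do not apply, but a 13-week total still cannot be split into two 4-week periods.

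**5. Whether the plan already uses period-specific work values.** Aim 3 does not say. The nearby specifications point away from it. The general model under Aim 1 gives its work-environment term no time index, and the Aim 2 growth models condition on baseline factor scores.

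**The case against.** The strongest reply is that the association model already contains shift type and overtime. A regression term adjusts the others whether it is labelled tested or controlled, and the surveys supply three values per nurse. This stands in part. A reader might infer that Aim 3 adjusts for fixed traits and nothing else, and the documents do not support that. The list of fixed controls belongs to the association model, not to the test across the three surveys, and the same sentence brings in the work environment factors. What remains open is whether those factors enter together or one at a time, and with baseline or repeated values. Even on the favourable reading, the test of change and the growth model name no work term.

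Three further points stand:

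- Only a net change biases the mean contrast, and nothing in the documents shows or predicts one.
- Overtime is not asked solely by quarter; the second item might be given a short window.
- Overtime worked in Weeks 4-8 is measured after Somni starts and could respond to better sleep, so adjustment might remove part of a real effect.

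It can also be said that this is an exploratory aim in a pilot. That limits the weight of the point, but it does not settle which analysis will be run.

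**Conclusion.** The point holds as a gap in specification and measurement. No Aim 3 analysis is stated to use period-specific shift type or overtime in the Somni contrast, and neither overtime item, as written, belongs to one 4-week period. A net change in working pattern could therefore be mistaken for a Somni effect or mask one.

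A reader might go further and infer that rota changes will be read as Somni effects. The documents do not support this, because it needs a net shift between the periods that they do not show. Under the assumed ranges the bias in mean sleep is 1.5 to 12 minutes, and it is zero if changes balance. The rise to 14% false rejections is specific to the assumed 40 nurses, 20-point fall in nights and 0.5-unit effect. The 31% and 69% figures hold only for a rolling 13-week window. The change is inexpensive and should be made before data collection.

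**What to change.** **TABLE 1 and surveys.** At baseline, Week 4 and Week 8, ask overtime hours, shift type or number of night shifts, and mean shift length *in the past 4 weeks*. The Week 4 and Week 8 answers then each belong to one comparison period. A count of night shifts also covers nurses who work both days and nights. A quarterly overtime item may be kept at baseline.

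**Aim 3.** Add a statement such as: *For PSQI, ring sleep, self-reported stress, HRV and C-SSRS, the before-after contrast will be reported unadjusted, and again with shift type, mean shift length and overtime for the same 4-week period as time-varying covariates.* State that the work terms enter jointly. Keep both results, because later overtime may itself respond to Somni.

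**Cost.** One or two survey items are reworded, night-shift count and shift length are given the same window, and a short SAP passage is added. No extra visit is needed. The adjusted model spends about three degrees of freedom (one each for shift type, shift length and overtime); how much that matters cannot be judged without a sample size.

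**Limit.** Season, staffing and other time trends stay confounded with Somni after this change, so the result should be described as uncontrolled pilot evidence.

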Aim 2. We will classify nurses into quartiles of high (top 25%), medium (middle 50%), and low (bottom 25%) HRV. We will use descriptive statistics to examine individual measures and composite scores of factors (sleep, stressful life events, psychiatric characteristics, work environment characteristics) and suicidal behavior [C-SSRS score]. To evaluate the change in suicidal ideation over time and the impact of each factor composite score, we will fit conditional latent growth curve models using 3 data points. The models will be expressed such that, given mean HRV and baseline composite scores for each factor category: $y_{it} = (\mu_a + \mu_\beta \lambda_t + \gamma_1 HCC_i + \gamma_2 WEC_i) + (\zeta_{ai} + \zeta_{\beta i} \lambda_t) + \varepsilon_{it}$ where y_{it} is the C-SSRS score for nurse i at time t , μ_a is the latent variable for the intercept value (baseline score), μ_β is the random latent variable for slope (growth over time) for nurse i multiplied by the vector of factor loadings specifying time, λ_{it} , ε_{it} is the time-specific residual for nurse i , ζ_{ai} and $\zeta_{\beta i} \lambda_t$ are random components of the latent intercept and slope variables, respectively. Sleep, stressful life events and psychiatric characteristics are fixed (time-invariant) predictors. The factor loadings for time on slope can be fixed to adjust for gaps in outcomes, which would allow for modeling more distant (e.g., 2025) data from baseline without increasing the number of timepoints included in the model. Further, we anticipate fluctuations in HRV over time. To accommodate the change in trend, we will explore both linear and quadratic growth functions. Baseline global sleep scores (PSQI), stressful life events, psychiatric and work environment characteristics will serve as predictors of suicidal ideation change over time. Individual nurse characteristics and psychiatric characteristic controls will be included as an interaction term to compare curves across nurses. To explore whether stress mediates the effect of predisposing factors on suicidal ideation, we will compare the models assessing the effect of predisposing factors on suicidal ideation with and without the mediator outlined by Barron and Kenny difference method which be used to gauge the size of the mediation effect.

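### Aim 3 models kit use and PSQI sleep together as predictors of C-SSRS without limiting PSQI to pre-kit values, so the part of the kit's effect that works through sleep can be adjusted away.

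*Combined protocol and SAP*

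**What the plan says.** The Exploratory Aim is stated as "To explore the preliminary impact of an existing sleep intervention" on stress, HRV, sleep and psychiatric outcomes, including suicidal ideation. Study Design, component 4, describes the kit as a "personalized sleep intervention aimed at promoting optimal sleep health". It is used in Weeks 4 to 8, and participants choose which items to use, when and for how long. PSQI and C-SSRS are collected at baseline, Week 4 and Week 8.

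The Aim 3 paragraph of the Statistical Analysis section has two parts that bear on this point:

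- A model is tested for each psychosocial and work environment factor, each kit component, "and the mean PSQI score while controlling for age, sex, gender, race, and history of psychiatric diagnosis". Its dependent variable is not named. The next sentence reads "We will repeat the same analysis modeling mean C-SSRS as the dependent variable".
- The growth curve sentence opens "To evaluate the change in suicidal behavior over time and the impact of global sleep (PSQI score) and each" and ends "sleep kit component (mean weekly frequency), we will fit conditional latent growth curve models". It gives no equation and no PSQI visit, and does not say whether PSQI is time-invariant or time-varying.

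Aim 2 is more specific about its own growth curve: "Baseline global sleep scores (PSQI), stressful life events, psychiatric and work environment characteristics will serve as predictors of suicidal ideation change over time", and "Sleep, stressful life events and psychiatric characteristics are fixed (time-invariant) predictors". The only mediation analysis in the plan has stress as the mediator.

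**The concern.** If the kit helps with suicidal ideation, the intended route is through better sleep. PSQI measured after the kit starts is then an intermediate outcome. A kit coefficient adjusted for it estimates only the effect that bypasses sleep, whereas the Exploratory Aim asks about the kit's overall impact. The better the kit works as intended, the more such a model understates it.

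Nothing in Aim 3 confines PSQI to pre-kit values. The mean PSQI score, if taken over the three visits, includes Week 8. No model of C-SSRS on kit use that is free of post-kit PSQI is specified. The pilot is meant to inform a fully powered study, so a misleading near-zero result on suicidal ideation would carry forward.

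**Working it through.** The plan gives no sample size, effect size or SD for Aim 3, so there is no figure of its own to reproduce. The check is an illustration in which every numerical value is assumed. The three visits and the Week 4 kit start come from the protocol.

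**Assumed model**

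- Kit use U has mean 0 and SD 1.
- PSQI at visit t is P_t = p + e_t, with Var(p) = 1 and Var(e_t) = 0.6² = 0.36. At week 8 it is lowered by aU, with a = 0.5.
- C-SSRS is Y_t = c + bP_t + noise, with b = 0.5, Var(c) = 1 and noise SD 0.6. At week 8 it is also lowered by dU, the effect not through sleep.
- True total effect at week 8 is −(ab + d). Full mediation (d = 0) gives −0.25. Half mediation (d = 0.25) gives −0.50.

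**Growth slope.** With equally spaced visits, the fitted change over 8 weeks is Y_8 − Y_0. The coefficient of U is:

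- No PSQI, or baseline PSQI: −(ab + d).
- Three-visit mean PSQI, time-invariant: e_8 − e_0 is uncorrelated with p + mean(e), because 0.36/3 − 0.36/3 = 0. The coefficient stays at −(ab + d).
- Week-8 PSQI: the share of the sleep-mediated part absorbed is 0.36/(1 + 0.36) = 0.265. The coefficient is −0.25 × (1 − 0.265) − d, which is −0.184 with d = 0 and −0.434 with d = 0.25.
- Time-varying PSQI: only −d remains.

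**Mean C-SSRS over three visits.** One visit in three carries the kit effect, so the coefficient is −(ab + d)/3 with no PSQI or with baseline PSQI. With mean PSQI it is −d/3.

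| Outcome and PSQI form | Full mediation | Loss | Half mediation | Loss |
|---|---|---|---|---|
| Slope, none or baseline | −0.25 | 0% | −0.50 | 0% |
| Slope, 3-visit mean | −0.25 | about 0% | −0.50 | about 0% |
| Slope, week 8 | −0.184 | 26% | −0.434 | 13% |
| Slope, time-varying | 0.00 | 100% | −0.25 | 50% |
| Mean C-SSRS, none or baseline | −0.083 | 0% | −0.167 | 0% |
| Mean C-SSRS, 3-visit mean | 0.000 | 100% | −0.083 | 50% |

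Large-sample simulation (one million nurses or more) agrees with each row. For the slope under full mediation, with N = 100 (assumed) and two-sided alpha 0.05 (sidedness assumed), power is 74% without PSQI, 75% with baseline, 73% with the three-visit mean, 44% with week 8 and 5% with time-varying PSQI. Under half mediation, time-varying PSQI leaves 69%.

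**Should PSQI be dropped altogether?** Kit use is chosen by the participant. Suppose poorer sleepers use the kit more (assumed correlation 0.4 with baseline PSQI) and the kit does nothing.

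- Slope, no PSQI: −0.5 × 0.4 × 0.36/√1.36 = −0.06, a spurious benefit, with 11% false positives at N = 100. Baseline PSQI gives 0.00 and 4%. Week-8 PSQI gives −0.12 and 24%.
- Mean C-SSRS, no PSQI: 0.5 × 0.4 × (1 + 0.36/3)/√1.36 = +0.19, a spurious harm. Baseline PSQI gives 0.00.

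Pre-kit PSQI therefore has a job to do in these models. PSQI measured after the kit starts does not do it reliably.

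**The case against.** A reader might infer that Aim 3 definitely adjusts for post-kit sleep, and that an effective kit will therefore look useless. The documents do not support that.

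- **PSQI timing.** The growth curve sentence names no visit. The only growth curve written out, in Aim 2, uses baseline PSQI as a time-invariant predictor of the same outcome. If Aim 3 inherits that form, nothing is lost. This stands, although Aim 3 neither refers back to Aim 2 nor repeats the restriction to baseline.
- **Mean PSQI.** The phrase belongs to the preceding model. Against the growth slope a three-visit mean costs about nothing. This stands for the growth curve, but not for the repeated mean C-SSRS model, where the same score removes the whole sleep-mediated part.
- **The repeated analysis.** Its first dependent variable is unnamed. If that variable was mean PSQI, then C-SSRS replaces it and PSQI drops out. This is possible, but PSQI is listed alongside the kit components as a term tested in the model, so carrying it over as a predictor is the more natural reading.
- **One joint model.** The text says models, in the plural, without an equation. Joint entry is likely but not stated.
- **Other evidence on the kit.** Component 4 plans to compare Weeks 4–8 with Weeks 1–4 on stress and suicidal ideation, with no PSQI adjustment mentioned. This is a partial safeguard. However, the three-time-point test in Aim 3 lists only sleep measures and kit use, not C-SSRS.
- **Direction.** Bias towards no effect is not assured, because self-selected use can push the estimate either way. This stands and shapes the fix.

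**Conclusion.** The point holds as a gap that leaves open forms of the model answering a different question from the Exploratory Aim. The loss ranges from none (baseline PSQI) to the whole sleep-mediated effect (time-varying PSQI, or mean PSQI in the mean C-SSRS model), with about 26% for week-8 PSQI under full mediation. A kit effect vanishes entirely only if it runs wholly through sleep and one of those last two forms is used. If half runs through sleep, half of the effect survives even then.

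These figures rest on assumed path coefficients, variances and sample size. The 26% in particular follows from the assumed ratio of within-nurse to total PSQI variance. That post-kit PSQI removes a sleep-mediated effect, and pre-kit PSQI does not, follows from the order in time and not from those values.

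Severity is moderate: the aim is exploratory, in a pilot, with no hypothesis attached.

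**What to change.** State in Aim 3 that every model of C-SSRS on kit use adjusts for pre-kit PSQI only. The adjustment should be required, because kit use is self-selected. Baseline PSQI qualifies without further conditions. Week 4 PSQI qualifies if that survey is completed before the kit is first used, and the text should say so.

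Report any model that includes PSQI measured after Week 4 separately, with its kit coefficient labelled as the *effect not through sleep*, or as part of a stated mediation analysis. Name the dependent variable of the first Aim 3 model, so that it is clear what is repeated for mean C-SSRS.

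The cost is a few sentences in the plan and one extra exploratory model to report. No new data are needed.
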